10.1.6 SAFETY OVERSIGHT

Safety oversight will be under the direction of a Safety Monitoring Committee (SMC) composed of individuals with the appropriate expertise, including a Biostatistician and an HIV Therapy clinician. Members of the SMC are independent from the study conduct and free of conflict of interest.

The SMC advises the study PI and protocol team for this Phase I study. The primary responsibility of the SMC is to monitor human subject safety. The SMC considers study-specific data as well as relevant background information about the disease, test agents, and target population under study.

During the trial the SMC will review:

- Real-time and cumulative safety data for evidence of study-related adverse events;
- Adherence to the protocol;
- Factors that might affect the study outcome or compromise the trial data (such as protocol violations, losses to follow-up, etc.).
- Review the achievement of enrollment benchmarks

The SMC will receive monthly reports via email for review and comments. The SMC will be contacted directly via email (and possibly via teleconferencing) for any event or situation that impacts participant safety throughout the study and specified interventions or study participation will be suspended or terminated dependent on the response of the SMC.

Safety Pause

Administration of the study products and new enrollments will be paused by the PI according to the criteria noted below if any of the following occur:

- a) Two or more participants experience a primary safety outcome measure that is a Grade ≥ 3 AE possibly related to study treatment (other than self-limited Grade 3 solicited reactogenicity AEs); or
- b) One (or more) participant experiences a Serious Adverse Event (SAE) that is assessed as related to study product.

In the event of a pause, the Study Monitoring Committee (SMC) will be asked to review all safety data. Review will include the relation to study treatment of the event(s) thought by the core team to be a primary safety outcome. In the event of a pause, the FDA (IND) and the DAIDS Medical Officer (MO) will be promptly notified.

Criteria for Resuming the Study

Study product administration and enrollments would resume only if review of the AEs that caused the pause results in a recommendation to permit further study product administrations and study enrollments. The reviews to make this decision will occur as follows:

- Pauses for treatment-related SAEs: The DAIDS MO and the PI will consult with the FDA to conduct the review and make the decision to resume, amend, or close the study and will notify the IRB accordingly.
- Pauses for Grade 3 or higher treatment-related AEs: The DAIDS MO, with the PI and the Safety Monitoring Committee (SMC), will conduct the review and make the decision to resume, amend, or close the study for the Grade 3 or higher AEs that meet criteria for pausing the study. As part of the pause review, the reviewers will also advise on whether the study needs to be paused again for any subsequent events of the same type. The FDA and the IRB will be notified of Grade 3 or higher pause reviews and of the study protocol team decision.

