1 PROTOCOL SUMMARY

1.1 SYNOPSIS

Title: Phase I Study to Assess the Safety and Activity of Combination Therapy using a Novel Monoclonal Antibody, VRC07-523LS, and the Latency Reversal Agent, Vorinostat, to Reduce the Frequency of Latent, Resting CD4+ T Cell Infection in participants with HIV-1 infection suppressed on ART (The VOR-07 Study)

Study Description: Participants with HIV-1 Infection on ART with a CD4 T cell count ≥ 350 cells/mm³ and viral suppression for ≥ 24 months. Participants will receive two series of combination therapy consisting of one (1) intravenous (IV) dose of VRC-HIVMAB075-00-AB (VRC07-523LS) followed by 10 oral (PO) doses of Vorinostat (VOR) taken every 72 hours. Each series will last approximately 1 month and the two series will be separated by at least one month. Combination ART is (ART) maintained throughout the study.

Objectives:

Primary Objective:

1. To evaluate the safety and tolerability of combination therapy with VRC07-523LS and VOR in HIV-infected participants on ART.

Other Objectives:

1. Explore the effect of two cycles of VRC07-523LS and VOR on the frequency of latent, resting CD4+ T cell infection.
2. Explore the influence of VOR given with VRC07-523LS on low-level plasma viremia as measured by low level viremia assay in participants who maintain suppression on ART.
3. Compare HIV RNA expression within resting CD4+ T cells in HIV-infected participants on stable ART before and after combination therapy with VRC07-523LS and VOR measured at baseline (Step 1) and after the second series (Step 4).
4. Explore the impact of combined therapy with VRC07-523LS and VOR on the quantity of integrated proviral DNA quantification in T cell populations.
5. Characterize viral envelope sequences detected in plasma or cells that are not neutralized by VRC07-523LS from baseline to post-treatment with VRC07-523LS and VOR.
6. Evaluate the pharmacokinetics of VRC07-523LS combined with VOR and determine whether anti-drug antibody (ADA) to VRC07-523LS can be detected in recipients administered VRC07-523LS in combination with VOR.

Endpoints:

Primary Endpoint:

1. Safety: Occurrence of at least one \geq Grade 3 adverse event (AE) including signs/symptoms, lab toxicities, and/or clinical events that is possibly, probably, or definitely related to VOR or VRC07-523LS

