2. VOR –
 - a. 400 mg PO every 72 hours for 10 doses per series
(total of 20 doses of VOR 400 mg in the study)

In Step 1, all participants will undergo study screening and enrollment. Participants will complete a baseline Leukapheresis (#1). In order to advance to Step 2, participants must be found to have a baseline measurement of the frequency of resting CD4 T cell infection ≥ 0.3 infectious units per million (IUPM) determined by Quantitative Viral Outgrowth Assay (QVOA) (lower limit of detection is 0.3 IUPM), as a further decrease from this low frequency of infection cannot be definitively measured given the QVOA assay threshold.

These criteria assure that eligible enrolled participants will have a measurable endpoint, thus decreasing risk of study participation for participants who would not have a measurable outcome.

Participants progressing to Steps 2 and 3 will receive two series of a single VRC07-523LS infusion followed by multiple doses of VOR.

In the first series (Step 2), participants will receive one VRC07-523LS 40 mg/kg infusion (infusion #1) on Day 0 followed by the 1st dose of VOR 400 mg PO taken at home on Day 2. Participants will take VOR 400 mg PO every 72 hours for a total of 10 doses.

In the second series (Step 3), participants will receive one VRC07-523LS 40 mg/kg infusion (infusion #2) on Day 60 followed by the 1st (of the 2nd series of VOR) dose of VOR 400 mg PO on Day 62. As in the previous Step, participants will take VOR 400 mg PO every 72 hours for a total of 10 doses.

Step 4 consists of 2 visits. The post-study treatment leukapheresis (#2) will be completed 5 – 8 weeks after the 2nd VRC07-523LS infusion. The End of Study Visit (EOS) will be scheduled to 2 – 4 weeks following the final leukapheresis (#2) visit.

[figure not shown]
Study Duration: The study will take approximately 8 months to enroll up to 12 participants and will be completed, inclusive of data analysis within 18 months of the enrollment of the last participant.

Participant Duration: Each participant will be enrolled on the study for approximately 28 weeks.

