For all participants, baseline assessments will be performed before each infusion and assessments for Solicited AEs will be performed after each infusion. All Solicited AEs are graded according to the Division of AIDS Table for Grading the Severity of Adult and Pediatric Adverse Events, Corrected Version 2.1 dated July 2017.

The Solicited AE assessment period is 3 full days following each infusion per the SOE in Section 1.3. Participants are instructed to record symptoms using a daily symptom tool. The study coordinator and the participant will be in contact after the 3-day Solicited AE assessment period, or sooner if indicated. In general, a participant who self-reports any reaction following an infusion that is greater than mild is seen by a clinician within 48 hours after onset, unless the reaction is improving and/or has completely resolved. Clinic study staff will follow new or unresolved Solicited AEs present at day 3 to resolution.

Solicited AE assessments include assessments of systemic and local symptoms, and study product-related lesions.

Assessment of Systemic and Local Symptoms

Systemic symptoms to be assessed as solicited AEs include increased body temperature, chills, malaise and/or fatigue, headache, myalgia, arthralgia, nausea, urticaria, non-exertional dyspnea, non-exertional tachycardia (assessed by CRS staff, not by the participant), generalized pruritus, facial flushing, and unexplained diaphoresis.

Local symptoms include pain or tenderness at the infusion site. The daily maximum severity reached for each symptom during the assessment period is reported.

Body temperature is measured by oral or infrared thermometry and is reported in degrees Celsius. If temperature is measured in Fahrenheit, the conversion to Celsius should be documented in the participant's chart note. A measurement is taken once daily during the assessment period and should be repeated if participant is feeling feverish.

Assessment of Infusion Site

Typical infusion site reactions are erythema/redness and induration/swelling. The maximum horizontal and maximum vertical measurements for all infusion site reactions are recorded.

All infusion/injection site reactions are monitored until resolution. Areas greater than 25 cm² are followed daily; otherwise, the frequency of follow-up is based on clinician judgment.

VRC07-523LS Post Infusion Telephone Follow-Up

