Provide participant post-infusion symptom log and instructions for completion prior to leaving the clinic. Post-infusion assessment includes the following:

- Contact participant between Days 4 and 6 post-infusion in the manner pre-determined by study coordinator and participant
- Review the symptom log at Days 4-6 with participant
- Collect and reconcile the symptom log with the participant at the Day 7 visit following each infusion

Solicited AE Assessments

Participants will be given a “Post-infusion AE Assessment” tool to use as a memory aid for tracking AEs that occur during the 3 days following the infusion. Participants will record daily temperature and symptoms.

For this study, solicited AEs occurring during the 3 days after receipt of study agent will include:

Localized Symptoms	Systemic Symptoms
• Erythema (redness)	• Fatigue
• Local pain/tenderness	• Headache
• Warmth at infusion site	• Fever >37.7°C or 99.9°F
• Induration (hardening or formation of a crust or scab)	• Chills
• Itching (generalized and local)	• Rashes
• Swelling	• Myalgia
• Skin discoloration	• Arthralgia
• Skin damage (vesiculation or ulceration)	• Nausea
• Vomiting	• Malaise
• Urticaria	• Non-exertional dyspnea
• Facial flushing	• Non-exertional tachycardia
• Unexplained diaphoresis	

Participants will also record the highest measured temperature daily. Participants should be instructed to take their temperature at least once daily, starting with the day of infusion (day 0), after leaving the clinic and through day 3 post-infusion.

Temperature should be taken orally or via infrared thermometry and in the evening whenever possible. If more than one measurement is made in a day (for example, due to feeling unwell), then the highest temperature taken that day should be recorded.

Participants will have a telephone interview with a study coordinator 4 -6 days following each VRC07-523LS infusion to review the solicited AE assessment tool. Any incidents or events identified that could be related to the infusion and are still unresolved after Day 3, will require participants to come into clinic for clinical assessment. Telephone conversation will be documented and signed off by the study PI.

Events occurring during the Solicited AE Assessment period that may require a clinic visit based on the judgment of a study clinician include:

- Rash,
- Urticaria,
- Fever of 38.6°C (Grade 2) or higher lasting greater than 24 hours,

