- A significant impairment in the activities of daily living (such as those consistent with Grade 2 or higher impairment),
- Arthralgia or other clinical concerns

The study coordinator reviews symptom logs for accuracy and completeness and will collect log at the Day 7 and Day 67 visits. Additionally, participants will undergo clinical laboratory assays and clinical

evaluations to assess safety at every visit. Participants will also be asked to contact the study coordinator, or study PI or designee should they experience any adverse events at any time points during the study.

Reactogenicity Assessment

The participant will assess for reactogenicity (expected) symptoms from days 0 to 3 following each infusion on their post-infusion symptom card.

The daily maximum severity reached for each symptom during the 3-day assessment period will be reported. Study staff will follow new or unresolved reactogenicity symptoms to resolution. In general, participants self-reporting any post-infusion reaction greater than mild are to be evaluated by Study PI (or designee) within 48 hours after onset, unless the reaction is improving and/or has completely resolved. Institute appropriate countermeasures, including medical intervention or procedures, if clinically indicated.

Estimated Blood Volumes Associated with the Study Visits

Visit or Week #	Blood Volume (mL)	Visit or Week #	Blood Volume (mL)
Visit 1	50	Visit 8 Day 60	116
Visit 2	153	Visit 9 Day 67	18
Visit 3 Day 0	61	Visit 10 Day 74	18
Visit 4 Day 7	15	Visit 11 Day 89	173
Visit 5 Day 14	16	Visit 12	50
Visit 6 Day 29	158	Visit 13	135
Visit 7	70		

Cancer Registry

All participants who receive greater than 8 doses of VOR in a study are asked to enter a study cancer registry. The registry is maintained by the clinical program director of the UNC HIV Cure Center. Participants willing to participate in the registry are contacted annually for 5 years following the completion of their VOR dosing regimen. The UNC Cancer Registry is searched annually for new cancer diagnoses registered to any of the VOR recipients. Data on participants included in this registry will be provided in the Annual Reports to the FDA for this study.

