9.2 SAMPLE SIZE DETERMINATION

We will enroll up to 12 fully evaluable participants (who receive two cycles of VRC07-523LS and VOR) to examine the effect of adding VOR and VRC07-523LS to ART on persistent replication-competent HIV within resting CD4+ T cells.

Any participant who does not complete both series of VRC07-523LS and VOR and the leukapheresis in Step 4 for reasons other than a grade 3 or higher AE will be replaced, to ensure up to 12 evaluable participants for safety.

Since the trial will be stopped if two participants experience a study treatment-related toxicity of Grade 3 or higher, the criterion for safety is grade 3 or higher toxicity in no more than 1 of 12 participants in the study.

For n=12 participants, if there are no primary AEs, then the exact 95% 1-sided upper confidence limit (UCL) for the true AE rate will be 0.22. Thus, if no AEs are observed, one can confidently rule out event rates greater than 22%.

All other analyses are therefore equally exploratory.

Because a focus of the study is on safety and potential AEs, accrual will be staggered such that enrollment and treatment administration will include a maximum of 1 participant per week.

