9.4.2 ANALYSIS OF THE PRIMARY SAFETY ENDPOINT

Safety:

For the primary safety analysis, AEs attributed to study treatment will be described through the end of study visit approximately 20 weeks after getting their first infusion at Day 0. All participants who have been exposed to at least one dose of study treatment will be included in this analysis.

Since the trial will be paused for SMC review if two participants experience a study treatment-related toxicity of Grade 3 or higher, the criterion for safety of this study is grade 3 or 4 toxicity in no more than 1 of 12 participants.

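### The two-participant Grade 3 rule is stated three ways: 9.2 and 9.4.2 carry no exemption, 10.1.6(a) does, so the 1-of-12 safety criterion can be exceeded without triggering the pause in 10.1.6(a)

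*Combined protocol and SAP*

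**What the plan says.** The primary endpoint (1.1 and 3) is at least one Grade 3 or higher adverse event "possibly, probably, or definitely related to VOR or VRC07-523LS". It has no exemption for solicited symptoms.

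The two-participant rule appears in three places:

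- 9.2 bases its safety criterion on this premise: "Since the trial will be stopped if two participants experience a study treatment-related toxicity of Grade 3 or higher". It concludes that Grade 3 or higher toxicity may occur in no more than 1 of 12.
- 9.4.2 reaches the same 1-of-12 criterion from a different premise: "Since the trial will be paused for SMC review if two participants experience a study treatment-related toxicity of Grade 3 or higher".
- 10.1.6(a), under Safety Pause, has the PI pause dosing and enrollment when two or more participants have a primary safety outcome of Grade 3 or higher "possibly related to study treatment (other than self-limited Grade 3 solicited reactogenicity AEs". Rule (b) separately pauses for one related SAE, with no exemption.

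Neither 9.2 nor 9.4.2 mentions the exemption or refers to 10.1.6.

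Solicited symptoms are defined by name and time. 8.1 gives one list: "Systemic symptoms to be assessed as solicited AEs include increased body temperature, chills, malaise and/or fatigue, headache, myalgia, arthralgia, nausea" and others. 8.2 gives a longer one, introduced by "For this study, solicited AEs occurring during the 3 days after receipt of study agent will include". The reactogenicity paragraph of 8.2 has the participant assess "reactogenicity (expected) symptoms from days 0 to 3 following each infusion". Vorinostat (VOR) starts inside that window: the first infusion is "on Day 0 followed by the 1st dose of VOR 400 mg PO taken at home on Day 2", and the second series repeats this on Days 60 and 62.

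**The concern.** A pause rule should give one answer to one set of facts. Here the premise that supports the 1-of-12 criterion in the statistical section is not the rule that operates in the oversight section. If two participants each have a self-limited Grade 3 solicited symptom judged related, the PI can read three different instructions, and the argument that the pause rule keeps the trial at or below 1 of 12 no longer follows.

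The exemption is also open on attribution. 10.1.6(a) speaks of study treatment, which is both drugs, whereas the parallel exception in 7.2 is limited to discontinuing VRC07-523LS. Nausea and fatigue, named first among VOR effects in 2.3.1, are on both solicited lists. The primary objective is the safety of the combination, and the Day 2 dose is the first combined exposure.

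**Working it through.** **1. The plan's own figure.** For 0 events in 12, the exact one-sided 95% upper limit is 1 − 0.05^(1/12) = 0.2209, which agrees with the 0.22 in 9.2. This limit concerns primary events. Since the primary endpoint has no exemption, the exemption does not change it.

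**2. One case under each rule.** Suppose two participants each have a self-limited, non-serious Grade 3 solicited symptom judged related to study treatment.

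| Provision | Result |
|---|---|
| Primary endpoint (1.1, 3) | Both count |
| Criterion, at most 1 of 12 (9.2, 9.4.2) | Exceeded: 2 of 12 |
| Rule in 9.2 | Stop |
| Rule in 9.4.2 | Pause for SMC review |
| Rule (a) in 10.1.6 | No pause: neither event counts |
| Rule (b) in 10.1.6 | No pause: no SAE |

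The wording of 10.1.6(a) confirms the gap: it takes the primary safety outcome and then removes a subset. Exempt events are primary events by construction. This holds whichever drug the exemption was meant for.

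**3. Overlap with VOR.** At 72-hour intervals the doses fall on Days 2, 5, 8, …, 29 and 62, 65, …, 89. The symptom windows are Days 0–3 and 60–63. Doses inside them are Day 2 and Day 62, so 2 of 20. Of the 13 VOR effects named in 2.3.1, nausea and fatigue are on the 8.1 list, and vomiting is added by the 8.2 list (2 or 3 of 13). Self-limited Grade 3 nausea on Day 3 could be left out, while the same event after the Day 5 dose would count.

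**4. How much the exemption could matter.** The documents give no rate for this combination. In 2.2, severe systemic symptoms are reported in 3 VRC01 recipients in an 88-person trial, but that is another antibody. For VRC07-523LS itself, 2.3.1 reports no Grade 3 or higher event so far. The table is therefore illustration only. Assume that p is the chance that a participant has a primary event, and f the share of such participants whose only primary events are exempt. The chance of at least 2 of 12 is 1 − (1−q)^12 − 12q(1−q)^11, with q = p for the unexempted rule and q = p(1−f) for 10.1.6(a).

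| p | No exemption | f = 0.25 | f = 0.50 |
|---|---|---|---|
| 0.10 | 0.34 | 0.23 | 0.12 |
| 0.20 | 0.73 | 0.56 | 0.34 |
| 0.30 | 0.91 | 0.79 | 0.56 |

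Over this assumed grid the two rules differ by about 12 to 38 percentage points. Neither p nor f can be estimated from the documents.

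**5. The VOR part cannot be sized.** Section 2.3.1 reports only mild related toxicity in about 23 people at this site, with an average of 14 doses for most. Treated as 0 of 23, the one-sided 95% bound for Grade 3 is 1 − 0.05^(1/23) = 0.122. That bound covers all toxicity, laboratory events included, over whole courses. Spread evenly, two doses carry 0.122 × 2/14 = 0.017, and the chance of at least 2 of 12 is 1.8%. With half the risk on those two doses it is 0.122/2 = 0.061 and 16%. The range reflects the assumed split, not data.

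**The case against.** The strongest reply is that 10.1.6 is plainly the operative text. It names who acts, on what and how dosing resumes, while 9.2 and 9.4.2 merely summarize it to introduce a criterion. A PI is unlikely to treat the word *stopped* in 9.2 as a separate order. That is fair as to likely conduct. It does not repair the derivation, because the summary omits the one feature that makes the criterion and the pause diverge.

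On VOR, a reader might infer that the protocol exempts VOR toxicity from the pause. The documents do not support that. Section 8.2 ties reactogenicity to the infusion, 7.2 limits its exception to the antibody, and no section calls a VOR effect reactogenicity. An infusion-only intent is plausible; what stands is that 10.1.6(a) does not say so.

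A reader might also infer that such events would escape oversight. They would not. Under 8.3.5 the protocol team and the DAIDS Medical Officer are told within 24 hours of a related Grade 3 event, continued dosing is decided in consultation with the SMC, and related Grade 3 or 4 systemic reactions end further infusions and VOR doses for that participant. Under 10.1.6 the SMC gets monthly reports, is contacted directly about events that affect participant safety, and its response can lead to suspension. Grade 4 events, related SAEs, laboratory toxicities and unlisted symptoms still count toward a pause, and accrual is at most one participant per week. One limit on this reply is that 8.3.5 expressly requires SMC notification of a Grade 3 event only if it has not returned to Grade 2 or below within two weeks, which a self-limited event would usually have done.

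**Conclusion.** The inconsistency is real and should be corrected. It follows from the text alone: two participants with exempt events exceed 1 of 12 under the primary endpoint, and 9.2, 9.4.2 and 10.1.6(a) then prescribe a stop, a pause and no pause. The VOR point is secondary. The wording permits the broader reading without compelling it, and it concerns 2 of 20 doses and two or three listed symptoms.

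What is at risk is the automatic trigger, not safety oversight, the primary endpoint or the 0.22 limit. The probabilities above rest on assumed rates and splits and should not be quoted as estimates. Confidence is high on the inconsistency and moderate on its practical weight.

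**What to change.** - **9.2 and 9.4.2:** replace the restated rule with *paused for SMC review per 10.1.6*, removing *stopped* from 9.2. State that the 1-of-12 criterion counts all related Grade 3 or higher events, including those exempt from the pause.
- **10.1.6(a):** limit the exemption to *self-limited Grade 3 solicited symptoms that begin within 3 days of a VRC07-523LS infusion and are not assessed as related to VOR*.
- **Symptom lists:** do not widen the exempt set. In particular, do not settle on the longer 8.2 list for this purpose, since it adds vomiting, rashes and skin ulceration to what 8.1 names.

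No new data are needed, because 8.3.3.2 already requires causality for each drug separately. The cost is that the exemption will apply less often after the Day 2 and Day 62 doses, when both drugs are plausible causes, so an extra pause may occur. Missed VOR doses are not made up (2.3.1). On a 72-hour schedule, an assumed 7-day pause costs a participant who is mid-series 2 or 3 of 20 doses. A pause could also push an infusion outside its window, or lead to a replacement under 7.2.
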